### **3.4 Premature Termination of Study / Closure of Center**

The sponsor has the right to terminate this study, and the investigator/sponsor has the right to close a clinical site, at any time, although this should occur only after consultation between involved

parties; the IRB must be informed in any case. Should the clinical site be closed prematurely, all study materials (equipment, study medication, etc.) must be returned to the sponsor.

This study will discontinue due to medical or administrative reasons such as:

- Serious adverse events probably related to study drug administration so that the use of study drug may no longer be justifiable
- 2 or more deaths are observed during any point in the trial
- 5 or more adverse drug reactions (NCI-CTCAE  $\geq$  Grade 3) on the injected joint are observed during any point in the trial
- Significant change of benefit-risk ratio for the subjects
- Sponsor discontinues the investigation of JointStem for the treatment of osteoarthritis or determines that the doses being studied are no longer justifiable

Possible reasons for closing of a clinical site include the following:

- The investigator feels that the number or severity of adverse events is excessive
- A change of technical, administrative, or personal circumstances occurs and the conduct of the study no longer meets ICH-GCP guidelines
- In case of evident, significant non-compliance to protocol or poor data quality

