### **3.5 Treatment**

#### **3.5.1 Treatment to be Administered**

At Visit 2 (Week -5), a subject, who is qualified for this study, will be randomized to one of two study groups and the adipose tissue will be harvested via liposuction. At Visit 3 (Week 0, baseline), the randomized subject will receive a single intra-articular injection.

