### **3.5.8 Treatment Compliance**

Only subjects who are randomized to JointStem will return on Visits 4, 5, 6, 7 and 8 (Months 1, 3, 6, 9 and 12) or at Early Termination. On the other hand, subjects who are randomized to the positive control group will only return on Visits 4, 5 and 6 (Months 1, 3 and 6) or at Early Termination.

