## **7.3 Serious Adverse Event Reporting Procedures**

Serious adverse events will be collected and recorded from the drug administration to 3-month follow-ups.

Serious Adverse Events, including laboratory test abnormalities fulfilling the definition of serious, after the first dose, and during follow-up period must immediately (within 24 hours of the investigator’s awareness) be reported to the person/parties as detailed in the study file. A Serious Adverse Event form must also be completed within 1 day of the investigator’s awareness and

forwarded to the designated person/parties as detailed in the study file. Each Serious Adverse Event must be followed up until resolution or stabilization by submission of updated reports to the designated person/parties.

Serious adverse events also will be collected and reported within 1 working day of discovery or notification of the event if it occurs 7 days after the last dose of study drug or after the end of the study and is thought to be possibly related to study drug.

For all deaths, available autopsy reports and relevant medical reports should be faxed to Sponsor or their designee. For this reporting process, subject assessments must be made 7 days after administration of the last dose of study drug.

If a subject is permanently withdrawn from the study because of a serious adverse event, this information must be included in the initial or follow-up Serious Adverse Event Report Form as well as the End of Study Case Report Form.

When required, and according to local law and regulations, serious adverse events must be reported to the institutional review board and Regulatory Authorities.

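### Protocol section 7.3 puts serious adverse events after Day 7 under two reporting rules and does not say which one governs

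*Protocol*

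**What the plan says.** Protocol section 7.3 has four statements that bear on this point.

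- The opening sentence sets a collection window: "Serious adverse events will be collected and recorded from the drug administration to 3-month follow-ups".
- The second paragraph covers SAEs "after the first dose, and during follow-up period must immediately (within 24 hours of the" investigator becoming aware of them. It has no relatedness condition.
- The third paragraph provides for further SAE collection, with events "reported within 1 working day of discovery or notification of the event if it occurs 7 days after the last dose of study drug". It applies the same rule once the study is over. Its condition is that the event "is thought to be possibly related to study drug".
- The fourth paragraph asks for autopsy and medical reports on all deaths to go to the sponsor, with no deadline. It also refers to subject assessments 7 days after the last dose.

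Elsewhere, Protocol 3.5.1 says that "the randomized subject will receive a single intra-articular injection". Protocol 3.4 lists as a reason to discontinue the study that "2 or more deaths are observed during any point in the trial". An adjacent reason does depend on causality: "Serious adverse events probably related to study drug administration". Protocol 7.2 requires all adverse events after the first dose to be reported on the eCRF. SAP 8.2 states that no data and safety monitoring board (DSMB) is planned.

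**The concern.** A boundary of 7 days after the last dose makes sense where dosing is repeated: a strict rule applies during treatment and a lighter one once treatment has stopped. Here the first dose is the last dose, so the boundary falls one week after the only injection. From then on the same in-study SAE fits both the second and the third paragraph, with different clocks and different scope.

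What is at stake is how quickly the sponsor hears of an event. A site that takes the third paragraph as the rule after Day 7 has a longer clock for related SAEs. It may also see no duty to expedite an event it considers unrelated, including a death. The two-death criterion in 3.4 counts deaths of any cause, and there is no DSMB to look at accumulating events independently.

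**Working it through.** The documents give no figure on this point to reproduce. The check compares the rules and measures how long they overlap.

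**1. The two rules side by side**

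| | 7.3, second paragraph | 7.3, third paragraph |
|---|---|---|
| Period | From first dose, through follow-up | From 7 days after last dose, or after end of study |
| Clock | 24 hours from awareness | 1 working day from discovery or notification |
| Relatedness | No condition | Possibly related |

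No sentence ranks one above the other. Under Protocol 7.2.1 the investigator answers the relatedness question Yes or No. A No at the site is therefore enough to place an event outside the third paragraph.

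**2. Length of the overlap**

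Inputs: one injection at Visit 3 (Protocol 3.5.1). Control follow-up ends at Month 6 unless the subject leaves early, since Protocol 3.5.8 says that "subjects who are randomized to the positive control group will only return on Visits 4, 5 and 6 (Months 1, 3 and 6". JointStem follow-up runs to Month 12 (Protocol 3.5.3 and 3.5.8). One month is taken as 365.25/12 = 30.44 days.

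Share of follow-up after Day 7 = (D − 7)/D, where D is the length of follow-up in days.

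- To Month 6: (182.6 − 7)/182.6 = 96.2%
- To Month 12: (365.25 − 7)/365.25 = 98.1%
- To Month 3, the end of the window in the opening sentence: (91.3 − 7)/91.3 = 92.3%

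The first scheduled visit after injection is Month 1 ± 3 days, so no earlier than about day 30.4 − 3 = 27.4. Every scheduled follow-up visit falls in the overlap.

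**3. Difference in clock**

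Take awareness on a Friday evening and assume a Monday-Friday working week. The 24-hour limit expires on Saturday evening. One working day runs to Monday evening, which is 3 × 24 = 72 hours after awareness.

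**4. Difference in scope**

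An SAE or death after Day 7 that the site judges unrelated must be reported within 24 hours under the second paragraph. The third paragraph alone gives it no expedited deadline. In 3.4 the SAE criterion carries a relatedness condition and the death criterion does not, so an unrelated death counts toward the two.

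**5. Whether removing the 7-day trigger alone would be enough**

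It would not. The third paragraph would then start only at the end of the study, which Protocol 3.5.3 places at the last subject's Visit 8. A control subject's scheduled visits end at Month 6. A possibly related SAE in that subject at, say, Month 8, with the study still running, would be past the subject's own follow-up and before the end of the study. The 7-day trigger covers that event now, and the bare deletion would remove the cover.

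**The case against.** The strongest reply is that the two paragraphs do not conflict. The third says SAEs will *also* be reported and never says that *only* possibly related ones are. A site that reports every SAE within 24 hours satisfies both. This reading is available and may be what was meant. On it, however, the 7-day trigger does no work during follow-up, because the second paragraph already covers those events sooner and without a relatedness filter. The text is then redundant in study instead of contradictory, and a site still has to work out which was intended.

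A reader might also infer more than the documents support:

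- **That SAEs would be missing from the SAP tables.** The SAP builds its summaries from eCRF data (SAP 2.1 and 7.1). Protocol 7.2 requires all adverse events after the first dose on the eCRF regardless of cause, and events are recorded at each visit from Visit 3 to Visit 8. The third paragraph of 7.3 limits none of this.
- **That unrelated deaths would never reach the sponsor.** The fourth paragraph of 7.3 asks for reports on all deaths without a relatedness condition. It sets no deadline, so the question of timing remains.
- **That expedited reports are the sponsor's main source of information.** The documents do not say so. Monitoring visits with eCRF review (Protocol 4.3) and data confirmation for each subject at Month 6 are other routes, though slower.
- **That 96% and 98% measure harm.** They are shares of calendar time in which two rules overlap. They say nothing about how many events would be reported late.

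**Conclusion.** The point holds as an unresolved overlap between two reporting rules. After Day 7 an in-study SAE meets the terms of both, and the protocol does not say which prevails. The overlap is about 96% of follow-up to Month 6 and 98% to Month 12.

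The consequence is conditional on a site treating the third paragraph as the governing rule. A related SAE could then be notified up to about 72 hours after awareness instead of 24, given a Monday-Friday week. A death judged unrelated might not be expedited although 3.4 counts it. The effect is on prompt notification, and so on how soon the two-death criterion can be applied. The documents do not support the stronger conclusions that the third paragraph overrides the second or that the SAE tables would be incomplete because of it.

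This is separate from the 3-month sentence that opens 7.3: removing that sentence would leave the overlap in place. The correction is still worth making, because it is cheap and concerns safety reporting in a trial without a DSMB.

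**What to change.** Reconcile the paragraphs of 7.3 in one protocol amendment.

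1. State that the second paragraph governs all SAEs and all deaths, regardless of relatedness, from injection to the subject's own last scheduled visit. Define that visit as Visit 6 for control, Visit 8 for JointStem, or the Early Termination or Final Follow-up visit where one applies. The optional Month 24 visit is not part of this definition; the Schedule of Assessments lists no adverse event assessment there.
2. In the third paragraph, replace both triggers (7 days after the last dose, and the end of the study) with a single one: the event occurs after the subject's last scheduled visit. Control subjects between Month 6 and the end of the study then stay covered for possibly related events.
3. Align the opening 3-month collection sentence in the same edit. Otherwise it would contradict the period in item 1, because Month 3 is half of the control arm's 6 months and a quarter of the JointStem arm's 12.

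The cost is a short amendment and a notice to two or three sites. Sites may file a few more unrelated SAE reports in a 30-subject trial. No visit, assessment or analysis changes.

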## **8. USE OF DATA AND PUBLICATION**

All data and results and all intellectual property rights in the data and results derived from the study will be the property of the sponsor, who may utilize the data in various ways, such as for submission to government regulatory authorities or disclosure to other investigators. The investigator, while free to utilize data derived from the study for scientific purposes, must discuss any publication with the sponsor prior to release and obtain written consent of the sponsor on the intended publication. The sponsor recognizes the right of the investigator to publish the results upon completion of the study. However, the investigator must send a draft manuscript of the publication or abstract to the sponsor thirty days in advance of submission in order to obtain approval prior to submission of the final version for publication. This will be reviewed promptly and approval will not be withheld unreasonably. In case of a difference of opinion between the sponsor and the investigator(s), the contents of the publication will be discussed in order to find a solution that satisfies both parties.

The investigator is encouraged to participate in the evaluation of the data for scientific purposes but is expected to work with the sponsor in the development of any scientific presentation or publication. Since the sponsor authors will be included, it is expected that all co-authors of the manuscripts will have an opportunity for feedback in the content and conclusions. The technical and editorial resources of the sponsor will be available to assist in the development of abstracts, presentations, and publications regarding this study and it is expected that drafts will be sent to the sponsor with adequate time for input and revisions prior to submission.

Appendix 7. International Knee Documentation Committee (IKDC) Subjective Knee Evaluation

Appendix 8. RAND 36 Questionnaires

Appendix 9. MRI Final Evaluation

## Appendix 1. Laboratory Parameters

Blood and urine samples for complete laboratory evaluation (hematology, serum chemistry, and urinalysis) at Visits 1, 3, 4, 5, 6, 7 and 8 (Screening, Baseline, M1, M3, M6, M9 and M12) or Early Termination or Final Follow-up Visit.

HEMATOLOGY	CHEMISTRY	URINALYSIS
Hemoglobin	Total bilirubin	Color
Hematocrit	Alkaline phosphatase	Appearance
RBC	ALT (SGPT)	Specific gravity
WBC	AST (SGOT)	pH
MCV	Blood urea nitrogen (BUN)	Protein
MCH	Creatinine	Glucose
MCHC	Glucose	Ketones
Neutrophils (absolute)	Albumin	Bilirubin
Lymphocytes (absolute)	Total protein	Blood
Monocytes (absolute)	Sodium	Leukocyte esterase
Eosinophils (absolute)	Potassium	WBC
Basophils (absolute)	Chloride	RBC
Platelets	Bicarbonate	Epithelial cell
PT-INR	Calcium	Bacteria
	HCG *	Hyaline casts
	HIV **	

\* HCG (pregnancy test) only for all females of childbearing potential (please refer to the relevant inclusion criteria) at Visits 1, 6 and 8 or Early Termination or Final Follow-Up Visit.

\*\* Visit 1 only

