### Schedule of Assessments

	Screen.	Harv.	Treat.	1 st Follow-up				2 nd Follow-Up		Long-term	
Blinding	N/A	Double Blinding							Open 		Follow-up
Visit	1	2	3	4	5	6	ET	7	8	N/A	
Week / Month	W-7	W-5	0	M1	M3	M6	<M6	M9	M12 or Final FU 	M24	
Informed consent	X										
Medical and Medication History	X	X									
Demographic information	X										
Complete physical examination	X		X		X	X	X 	X	X	X	
Vital signs and weight	X	X	X	X	X	X	X	X	X	X	
Hematology, serum chemistry, and urinalysis 	X		X	X	X	X	X 	X	X		
Pregnancy test 	X					X	X 		X		
HIV test for Screening	X										
12-lead ECG	X		X			X	X 		X		
X-ray	X										
Eligibility confirmation	X	X									
Randomization		X									
Liposuction		X									
Injection of final drug product			X								
AE and concomitant medication assessment			X	X	X	X	X	X	X		
Records of Treatment and Medications										X	
MRI scan 	X					X	X 		X	X	
WOMAC			X	X	X	X	X 	X	X	X	
VAS	X		X	X	X	X	X 	X	X	X	
Lysholm			X	X	X	X	X 	X	X	X	
KOOS			X	X	X	X	X 	X	X	X	
IKDC			X	X	X	X	X 	X	X	X	
Quality of Life (RAND-36)			X		X	X	X 	X	X	X	

1. See Appendix 1 for the complete list of laboratory tests
2. Serum pregnancy test is performed for all females of childbearing potential (please refer to the relevant inclusion criteria)
3. May be performed the day of Visit 2 or after due to scheduling or re-scanning.
4. Performed only if the early termination is after V3.
5. Performed only if the early termination is after V4.
6. Performed if the follow-up is discontinued after V6.
7. Only for JointStem group.

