##### **3.2.1 Inclusion Criteria**

- 1) Subject who can give written informed consent
- 2) Male or female of any race, aged 22-60
- 3) Subject who had osteoarthritis of knee diagnosed at least six months prior to Screening
- 4) Subject who has joint pain  $\geq$  40mm on VAS (Visual Analog Scale) at Screening
- 5) Subject who has swelling, tenderness and active range of motion  $\geq$  Grade I at Screening
- 6) Subject who seeks invasive interventions of intra-articular injections
- 7) Subject who is willing to discontinue all pain medications for osteoarthritis except rescue medication (< acetaminophen 3.25 g per day) at least 72 hours prior to screening and throughout the duration of study
- 8) Subject who has radiographic evidence of grade 3 to 4 osteoarthritis based on the Kellgren and Lawrence radiographic criteria.
- 9) Female subject who meets one of the following criteria
  - a. Female subject of non-childbearing potential:
    - Post-menopausal for at least 6 months; or
    - Surgically sterile

b. Female patients of child-bearing potential:

- Neither pregnant nor lactating; and
- Abstinent or use adequate contraception (2 forms of birth control, one of which must be a barrier method)

10) Subject who is able to comply with lifestyle guidelines, scheduled visits, treatment plan, laboratory tests, and other study procedures

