#### **Screening Visit 1 (Week -7)**

The following screening assessments/procedures must be performed and the results documented within approximately 7 weeks before Baseline visit unless otherwise indicated:

- Record demographic data (i.e., date of birth, race, height, and weight).
- Measure VAS (see Appendix 4).
- Record medical and medication history.
- Perform a complete physical examination.
- Measure vital signs (sitting blood pressure, pulse, breathing, and temperature).
- Measure 12-lead ECG.
- Collect blood and urine samples for hematology, serum chemistry, and urinalysis.
- Perform X-ray for Kellgren-Lawrence scale (see Appendix 2).
- Perform MRI to measure damaged cartilage area (Please follow the instruction separately provided by the sponsor). \* MRI may be performed the day of Visit 2 or after due to scheduling or re-scanning, as long as the results are confirmed prior to injection.

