### 4.2 Treatment Period

#### **4.2.1 Visit 2 (Week -5)**

For subjects who are preliminarily eligible for this study based on screening procedures, Visit 2 will occur within approximately 2 weeks ( $\pm$  4 days) after Visit 1. During this visit, the following assessments/procedures should be performed:

[figure not shown]
- Measure vital signs (sitting blood pressure, pulse, breathing, and temperature) and weight.
- Confirm medical and medication history.
- Determine the final eligibility.
- Randomize to one of two groups (Please follow the randomization instruction separately provided by the sponsor).

Subjects who are finally eligible will then be taken to the operation room for the procedure of liposuction.

- In sterile conditions, approximately 10 – 40 mL of fat will be harvested using the syringe liposuction technique with Tumescent (or super-wet) local anesthesia (Please follow the liposuction instruction separately provided by the sponsor).
- Ship the packaging box containing the harvested syringe to Biostar SCRI designated by the sponsor (pre-labeled).
- Dispense a concomitant medication note.

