1.3 SUMMARY OF THE STUDY DESIGN

1.3.1 General Study Design and Plan

This is a double-blind, randomized, controlled study to evaluate the efficacy and safety of JointStem for the treatment of osteoarthritis. Following a 2-week screening period, approximately 30 subjects will be randomly assigned into one of the following two arms in a 2:1 ratio (2 JointStem: 1 positive control):

- JointStem (1×10^8 cells/3mL)
- Positive control: Hyaluronic Acid

After each subject completes 6-month visit (Visit 6) and the data management team confirms all individual data have no issue, the individual database will be locked and the blinding will be

open for the statistical analysis. Only subjects who are randomized to JointStem group will then be scheduled for 9-month and 12-month follow-up visits (Visits 7 and 8).

The Schedule of Assessments is presented by Table 1.

Table 1 Schedule of Assessments

| | Screen. | Harv. | Treat. | 1 st Follow-up | | | | 2 nd Follow-Up | |
|--|---------|-----------------|--------|---------------------------|----|----|----------------|---------------------------|------------------------------|
| Blinding | N/A | Double Blinding | | | | | | Open ⁷ | |
| Visit | 1 | 2 | 3 | 4 | 5 | 6 | ET | 7 | 8 |
| Week / Month | W-7 | W-5 | 0 | M1 | M3 | M6 | <M6 | M9 | M12 or Final FU ⁶ |
| Informed consent | X | | | | | | | | |
| Medical and Medication History | X | X | | | | | | | |
| Demographic information | X | | | | | | | | |
| Complete physical examination | X | | X | | X | X | X ⁴ | X | X |
| Vital signs and weight | X | X | X | X | X | X | X | X | X |
| Hematology, serum chemistry, and urinalysis ¹ | X | | X | X | X | X | X ⁴ | X | X |
| Pregnancy test ² | X | | | | | X | X ⁴ | | X |
| HIV test for Screening | X | | | | | | | | |
| 12-lead ECG | X | | X | | | X | X ⁴ | | X |
| X-ray | X | | | | | | | | |
| Eligibility confirmation | X | X | | | | | | | |
| Randomization | | X | | | | | | | |
| Liposuction | | X | | | | | | | |
| Injection of final drug product | | | X | | | | | | |
| AE and concomitant medication assessment | | | X | X | X | X | X | X | X |
| MRI scan ³ | X | | | | | X | X ⁵ | | X |
| WOMAC | | | X | X | X | X | X ⁴ | X | X |
| VAS | X | | X | X | X | X | X ⁴ | X | X |
| Lysholm | | | X | X | X | X | X ⁴ | X | X |
| KOOS | | | X | X | X | X | X ⁴ | X | X |
| IKDC | | | X | X | X | X | X ⁴ | X | X |
| Quality of Life (RAND-36) | | | X | | X | X | X ⁴ | X | X |

1. See Appendix 1 for the complete list of laboratory tests

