7.2 CLINICAL LABORATORY PARAMETERS

Laboratory assessments (hematology, blood chemistry and urinalysis) are collected at Visits 1, 3, 4, 5, 6, 7 and 8 (Screening, Baseline, M1, M3, M6, M9 and M12) or Early Termination (only if the subject is early terminated after Visit 3) or Final Follow-up Visit:

- Chemistry: Total Bilirubin, Alkaline Phosphatase, Aspartate Aminotransferase (AST) (SGPT), Alanine Aminotransferase (ALT) (SGOT), Blood Urea Nitrogen (BUN), Creatinine, Glucose, Albumin, Total protein, Sodium, Potassium, Chloride, Bicarbonate, Calcium, HCG, HIV.
- Hematology: Hemoglobin, Hematocrit, RBC, WBC, MCV, MCH, MCHC, Neutrophils (absolute), Lymphocytes (absolute), Monocytes (absolute), Eosinophils (absolute), Basophils (absolute), Platelets, PT-INR.
- Urinalysis: Specific gravity, Color, Appearance, pH, Protein, Glucose, Ketones, Bilirubin, Blood, Leukocyte esterase, WBC, RBC, Epithelial cell, Bacteria, Hyaline casts.

All laboratory parameters will be presented in Système International (SI) units. Quantitative results (including actual value and change from baseline) will be summarized using descriptive statistics by baseline and post-baseline visit for each laboratory test group above. Laboratory test results were evaluated as normal, abnormal (not clinically significant) or abnormal (clinically significant). The number and percentage of subjects of each category will be summarized by time point, treatment and total for each parameter.

All laboratory data will be included in the listings. A pregnancy listing will be provided separately.

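### No pregnancy test is scheduled between Visit 1 and the injection at Visit 3, so the only pre-treatment result is nominally 49 days old at dosing

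*Protocol*

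**What the plan says.** Protocol Section 3.2.1, inclusion 9b, requires women of childbearing potential to be "Neither pregnant nor lactating; and" to be abstinent or use two contraceptive methods, one of them a barrier. Section 3.3 adds a mandatory withdrawal for a participant who has a baby while enrolled.

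Testing is set out in three places:

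- Protocol Appendix 1 restricts HCG to females of "childbearing potential (please refer to the relevant inclusion criteria) at Visits 1, 6 and 8 or Early Termination or Final Follow-Up Visit".
- The protocol's Schedule of Assessments marks the serum pregnancy test at Visits 1, 6 and 8 and at Early Termination. Its footnote 4 qualifies the last: "Performed only if the early termination is after V3".
- SAP Table 1 (Section 1.3.1) carries the same row: "Pregnancy test ² | X | | | | | X | X ⁴ | | X". The columns run Visit 1, 2, 3, 4, 5, 6, Early Termination, 7, 8.

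On timing, Section 4.1 asks for screening results "documented within approximately 7 weeks before Baseline visit unless otherwise indicated". Section 4.2.1 says "Visit 2 will occur within approximately 2 weeks" of Visit 1, with a tolerance of 4 days, and places the final eligibility decision, randomisation and liposuction at that visit. Section 4.2.3 allows up to 5 weeks from Visit 2 to the injection at Visit 3.

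**The concern.** Visit 3 is the last point at which a test can prevent the injection, and the injection cannot be undone. Inclusion 9b and the Section 3.3 withdrawal rule indicate that the protocol does not intend to treat pregnant women. Yet the schedule asks for no check of pregnancy status in the seven weeks between screening and dosing. The schedule marks eligibility confirmation only at Visits 1 and 2, and the Visit 2 check comes without a new HCG. After injection, the next scheduled test is at Month 6 unless the subject leaves early. What is at stake is participant safety; no endpoint, estimate or error rate is affected.

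**Working it through.** **1. Which tests fall before the injection.** Read column by column, the pregnancy-test row gives Visits 1, 6, 8 and Early Termination in both schedules, and Appendix 1 agrees. Early Termination testing requires that Visit 3 has passed. Visit 1 is the only test left before treatment.

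**2. Whether other text adds one.** The procedure lists for Visits 2 and 3 name no pregnancy test. That silence proves little alone, because the lists for Visits 1, 6 and 8 do not name it either; the schedules and Appendix 1 settle the matter. Appendix 1 does place HCG in the chemistry column, and chemistry is drawn at Visit 3, but the HCG footnote names its own visits and Visit 3 is not among them. SAP Section 7.2 ends its chemistry list with "Sodium, Potassium, Chloride, Bicarbonate, Calcium, HCG, HIV" and gives the collection visits as 1 and 3 to 8. It treats HIV the same way, although Appendix 1 and SAP Table 1 confine HIV to Visit 1. So this is a reporting list, not a schedule, and it requires no result before injection.

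**3. Age of the Visit 1 result.** Inputs: Visit 1 to Visit 2 is 14 days, tolerance 4 (Section 4.2.1); Visit 2 to Visit 3 is at most 35 days (Section 4.2.3).

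- At liposuction: 14 − 4 = 10 to 14 + 4 = 18 days.
- At injection, nominal: 14 + 35 = 49 days = 7 weeks, which reproduces the plan's Week −7 to Week 0.
- At injection, Visit 2 four days early and Visit 3 at 5 weeks: 10 + 35 = 45 days.
- At injection, both windows used in full: 18 + 35 = 53 days.
- At injection, if Visit 3 comes 3 weeks after Visit 2 (an assumption, since 5 weeks is only an upper limit): 10 + 21 = 31 to 18 + 21 = 39 days.

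The 53 days is a soft figure. Both the interval to Visit 2 and the 7-week screening limit are stated as approximate, and 53 days exceeds the nominal 49.

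**4. Effect of a Visit 3 test.** The age of the latest result at injection falls from 49 days nominal to 0.

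**The case against.** The strongest case against the point is that other safeguards make the event unlikely. Two-method contraception or abstinence is required, history and final eligibility are reviewed at Visit 2, and a physical examination takes place at Visit 3. The trial has about 30 subjects of either sex, aged 22 to 60, so most probably nobody would be affected. The sponsor's separate liposuction and injection instructions may already call for a test. All of this stands as a reason to keep the point in proportion. None of it establishes pregnancy status on the day of dosing. If the separate instructions do contain a check, the protocol's schedule should still show it.

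A reader might infer that injecting such a woman would breach inclusion 9b. The documents do not support that as a general statement. Eligibility is settled at Visit 2, and up to 35 of the nominal 49 days come afterwards; a pregnancy beginning then does not make the enrolment a breach. Inclusion 9b and Section 3.3 show intent, no more.

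A reader might also want a probability of exposure, or the share of pregnancies a new test would catch. Neither can be supported. The documents give no number of women of childbearing potential, no contraceptive failure rate and no detection lag. Any lag assumed would have to apply to the Visit 1 test too, since that test can also miss a very early pregnancy.

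**Conclusion.** The gap is real: no pregnancy test is scheduled after Visit 1 and before the injection, and the three places that set the testing visits agree. The measurable size is the age of the result at dosing: 49 days nominal, about 53 with both windows used in full, and less if Visit 3 is early. This assumes that sites follow the published schedule and that the unseen instructions add nothing.

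The frequency and severity of harm cannot be stated from the documents. This is a cheap improvement to participant safety, not a statistical defect.

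**What to change.** Add a same-day urine pregnancy test at Visit 3 for women of childbearing potential, with a negative result required before injection. Make the change in the Schedule of Assessments, Section 4.2.3, Appendix 1 and SAP Table 1. Adjust footnote 2 of both schedules, which now specifies a serum test. There is a precedent for such a condition: Section 4.1 allows a late MRI provided its result is confirmed before the injection.

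State that a subject who tests positive is not injected and is withdrawn, consistent with Section 3.3, and word that rule so that it plainly covers pregnancy. Under the existing definitions she stays in the Safety population, having been randomised and completed Visit 2. She falls outside ITT because she was not injected.

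Optionally, add the same test at Visit 2 before randomisation and liposuction. It could also catch pregnancies that were too early to detect at Visit 1. Keep the serum tests at Visits 1, 6 and 8, and say in SAP Section 7.2 that HCG and HIV follow the visits in Table 1.

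The cost is one inexpensive test per eligible woman at a visit where urine is already collected, with no extra visit. A same-day result avoids holding a product that Section 3.5.2 describes as stable for up to 1 week. The optional Visit 2 test needs a new urine sample. The downsides are an occasional withdrawal after liposuction, and that a very recent conception may still be missed.
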